8.2. Eligibility Criteria

Participants are included in the platform if they have all the REMAP-level inclusions and none of the REMAP-level exclusion criteria.

8.2.1. Inclusion Criteria for this Domain

Patients are eligible for this domain only if they have been scheduled for elective surgery at UPMC facilities and are being evaluated pre-operatively prior to surgery.

Other criteria include:

- Age \geq 60 years
- Age < 60 but evidence of comorbidity risk as represented by a Charlson Comorbidity Index of > 2 in 12 months prior to enrollment
- Able to take an oral medication in non-crushable pill form
- Women must be post-menopausal, which is defined as not having a menstrual period within the last 12 months

8.2.2. Exclusion Criteria from this Domain

Patients will be excluded from this domain, at the time of randomization, if:

- The treating clinician believes that participation in the domain would not be in the best interest of the patient

- Pre-existing diabetes type I or II
- Women of child-bearing potential
- Presently taking metformin or prior use in the past 6 months
- Evidence of an absolute or relative contraindication to Metformin therapy
 - Known allergy to metformin
 - Acute or chronic metabolic acidosis with or without coma
 - Hemodialysis, end-stage renal disease, or GFR < 45 in the prior 30 days
 - Ongoing treatment with therapy known to have significant drug-drug interaction with metformin (carbonic anhydrase inhibitors, cimetidine, gliptins)
 - History of lactic acidosis
 - History of excessive alcohol intake
 - Severe hepatic dysfunction

8.3. Interventions

8.3.1. Research Testing and Study-related Communications

The study team may contact the patient's health care providers (including their PCP) to notify of patient's involvement in the study. These communications may occur at various times throughout the study.

8.3.2. Study Drug Intervention

Patients will be randomly assigned to intention to receive one of the following study interventions.

- Placebo
- Metformin 500mg ER
- Metformin 1000mg ER
- Metformin 1500mg ER

The dosing of and route of administration of metformin are not specified in the protocol but the following guidance is provided:

- Doses will be oral
- Subjects will be instructed to take a dose once daily and complete all dispensed medication from the provided pill bottle

Metformin should be discontinued if the patient experiences a serious adverse event (SAE) that is thought to be related to the study drug and may be discontinued at the discretion of the treating clinician if continued treatment is not in the best interest of the patient.

8.3.3. Timing of Initiation of Intervention

The intervention is to begin on the day following the evaluation of the eligible and consented subject at the pre-operative clinic/surgeon's office. Daily oral doses will continue through the hospital admission for elective surgery. For patients without side effects, dosing will continue daily for 90 days after the surgical encounter.

Patients will be contacted between the pre-operative clinic/surgeon's office visit and surgery to evaluate study drug compliance as well as any adverse events associated with the study drug.

8.3.4. Duration of Administration of Study Drug

The duration of Metformin therapy is a complimentary research question in this domain. In the short course intervention, subjects will receive the study drug (metformin or placebo) within 7-28 days prior to the elective surgical encounter. In the intermediate course therapy, subjects will receive the study drug for 29-90 days prior to surgery. In the long course therapy, patients receive a longer course of study drug prior to surgery when the pre-operative evaluation occurs far enough in advance (e.g., >3 month). All patients will receive study drug for 90 days after the surgical encounter.

8.3.5. Temporary Suspension of Study Drug

If the patient should experience any of the following, study drug administration will be temporarily discontinued for 48 hours:

- Procedure involving the administration of contrast dye

8.3.6. Suspension of Study Drug at the Direction of the Treating Clinician

Study drug administration may be suspended at the direction of the treating clinician in the event a patient should experience a medical condition where it is felt there is a predisposition to renal impairment and/or tissue hypoxia.

8.3.7. Collection of Blood Samples

As part of this domain, blood samples may be collected over the course of a patient's participation in this domain. These blood samples will be processed and aliquoted for long-term storage in a biorepository which will permit the analysis of such aliquots at a future unspecified date. Collection of blood samples from patients participating in this domain will be attempted at the following timepoints:

- Pre-op clinic visit
- Day of surgery (often in pre-op holding area)
- After surgery
- Post-op Day 3 or immediately prior to hospital discharge if sooner
- Post-op clinic visit

Where possible, blood samples will be piggy-backed at the time of clinical draws or will be taken through established intravenous lines to minimize patient discomfort. If there is concern the collection of blood samples via the established intravenous line may jeopardize the patency of this line, the blood sample may be drawn directly from a patient's vein. Blood samples will be processed via standard operating procedures and aliquoted to permit long-term storage. These blood samples will be maintained by the Department of Critical Care Medicine for an indefinite period of time. Each aliquot will bear a unique code number which will permit matching to coded medical record information, while guarding patient identity. Aliquots may be used by investigators within the University of Pittsburgh/UPMC as well as by external investigators. Any request for the use of aliquots banked in the biorepository will need to be reviewed and approved by the Biorepository Steering Committee.

8.3.8. Collection of Samples for Microbiome Sub-study

There is interest to determine how the microbiome may change over the course of this study. For this reason, up to 1000 subjects participating in this domain may be asked to participate in a microbiome sub-study. This sub-study will attempt to collect stool samples of participants at 3 timepoints:

- prior to surgery
- during the inpatient hospital admission or following hospital discharge and within 5 days of surgery
- temporal to the post-op visit

Those stool samples collected prior to and after the inpatient hospital admission should be returned to study personnel via pre-paid mailing envelopes. Subjects participating in the microbiome sub-study may also undergo a rectal swab on the day of surgery.

8.3.9. Collection of questionnaires

To examine cognitive and/or motor changes over the course of the study, subjects may complete a series of questionnaires. All subjects participating in this domain will be scheduled to have questionnaires completed via telephone interaction prior to their surgery and 30 days (+/- 7 days) after their index surgery.

The following questionnaires should be completed during the telephone call prior to the index surgery:

- EQ-5D (quality of life)
- MoCA-BLIND
- Functional Activities Questionnaires (FAQ)

The following questionnaires should be completed during the 30-day telephone call:

- Post-discharge resource use questionnaire
- EQ-5D (quality of life)
- Return to work questionnaire

In order to assess motor function, up to 1/3 of subjects who are over the age of 65 and living within 20 miles of the primary research offices may be asked to attend a 90 day (+ 28 day) in-person visit (Motor Assessment Group). This visit should include questionnaires similar to those completed during the 30-day telephone call as well as motor assessments, specifically:

- Post-discharge resource use questionnaire
- EQ-5D (quality of life)
- Return to work questionnaire
- Functional Activities Questionnaires (FAQ)
- NIH Toolbox
 - Cognition Battery
 - 2 Minute Walk Test
 - Grip Strength

On a case-by-case basis, the study team may determine it best to collect these questionnaires via telephone interaction.

For those subjects who do not attend the 90 day in-person visit, the following questionnaires will be completed via telephone interaction at 90 days post-op (+ 28 days):

- Hospital readmission questionnaire (primary endpoint)
- EQ-5D (quality of life)
- Return to work questionnaire
- Functional Activities Questionnaires (FAQ)
- Cognitive battery (MoCA-BLIND, Hayling, and phone CAM)

To avoid in-study learning by patients, alternative versions will be administered for those questionnaires used at multiple timepoints.

If someone should indicate by their answer on the EQ-5D that they are extremely anxious or depressed, a member of the LTOC team will ask if the subject has discussed these feelings with their health care providers. If yes, no further action is taken.

Regarding monitoring for anxiety or depression in subjects as per the queries on the interviews, if the patient answers no, then a written communication would be sent to the patient's PCP and surgeon for the SPRY-related procedure to communicate the subject's 'feeling extremely anxious or depressed' response on the EQ-5D, the context of the EQ-5D administration (that is, administered in conjunction with a research study). The PI and study team would also be notified of the patient's response.

8.3.10. Muscle Biopsy Sub-Study

In collaboration with [name] of the University of Utah, who focuses his research on the cellular and molecular mechanisms of muscle growth, we intend to explore Metformin's effect on striated muscle growth and structure. Muscle atrophy is a common occurrence within an aged population, often attributed to the decreased mobility and disuse seen in older adults. This finding may be accelerated after surgery and prolonged immobility. [name] is currently investigating as part of a randomized clinical trial whether Metformin may mitigate muscle atrophy through its ability to improve insulin sensitivity via AMPK pathway blockade. [name] clinical trial¹⁸ compares metformin to placebo for individuals on bed rest for five consecutive days.

All subjects from the Motor Assessment Group who are willing are eligible for the Microbiome and Muscle Biopsy Sub-studies. We intend to expand upon [name] work by enrolling up to 200 subjects from the SPRY study to assess the potential effect of Metformin on striated muscle tissue structure. This will be particularly relevant to assess in our patient cohort who are at risk for accelerated muscle atrophy after surgical stress. Subjects involved in this sub-study may have up to 2 muscle biopsy samples taken at 2 separate timepoints- on the day of elective surgery while the patient is under anesthesia and during the Visit at 90 days (+ 28 days) after surgery following the administration of lidocaine. The 90-day muscle biopsy will occur in either the Radiology Procedure Unit B or on the 8th floor of Montefiore Hospital.

Determining Metformin's effect on muscle tissue may be evaluated by measuring muscle fiber cross sectional area and correlating to muscle strength. In addition, the myogenic potential of sample myotubes may be evaluated.

In addition, as changes in muscle mitochondrial respiration are often seen with muscle atrophy, there is interest to examine this aspect and Metformin's potential effect.

To further examine this aspect, Drs. [name], [name], and [name] would like to be able to retain some of the above-referenced samples from the up to 200 subjects from whom muscle biopsies are obtained to investigate questions related to mitochondrial respiration using fresh muscle tissue as well as to use frozen tissue for questions about lipid and protein metabolism.

Muscle biopsies will be performed by physicians on the study team experienced in muscle biopsies, specifically Drs. [name], [name], [name], and [name].

The muscle sample collection procedure involves using a needle to take a small piece of muscle tissue from the outside of the patient's upper leg, about 4-6 inches above the knee. Following cleaning of the skin, Lidocaine will be injected to minimize any pain. A small incision about the size of this dash “_” (1/4th of an inch) will be made in the skin, through which a needle about the size of the letter “O” is slowly inserted into the muscle. A piece of the muscle (0.125-0.5 gram) is then removed with the needle, the skin is closed with a steri-strip and a light dressing is applied then a pressure wrap is placed over the dressing.

For patients involved in the Muscle Biopsy Sub-Study, anti-coagulant medications will be held per their standard of care pre-op directions for the biopsy conducted on the day of surgery. For the 90-day muscle biopsy, patients will be advised to hold:

1. Apixaban, Rivaroxaban, Dabigatran, Edoxaban (also known as Eliquis, Xarelto, Pradaxa, Savaysa)—48 hours
2. Aspirin, coated or uncoated (also known as Bayer, Bufferin, Exedrin, Ecotrin, Ascriptin)---5 days
3. Clopidogrel, Ticagrelor, or Pragruel (also known as Plavix, Brilinta, Effient)---5 days
4. Warfarin (also known as Coumadin)---5 days
5. Aggrenox (also known as Dipyridamole and Persantine)---5 days
6. Ticlid (also known as Ticlopidine)---5 days
7. Agrylin or Xagrid (also known as Anagrelide)---5 days

The study team will confirm the patient has held these medications prior to performing the muscle biopsy.

Appropriate post-biopsy care instructions will be provided to patients and a contact person in case they experience signs or symptoms of concern.

The study team will also assure patients receive post-op care instructions from the clinical team as need per their surgery and length of stay.

For both biopsies timepoints, technicians working under the direction of the study team will process the specimens. Some of these muscle samples (or a portion of the sample) may be retained for local use and storage while the remainder of the samples may be analyzed by collaborators such as the University of Utah. These technicians will be responsible for the processing of tissue for local use as well as for the shipping of shipping of the frozen muscle biopsy samples and associated research data to collaborators such as the University of Utah, an identified collaborator, in batches. [name] will not store this tissue for long-term use.

8.4. Endpoints

8.4.1. Primary Endpoint

The primary endpoint for this domain is the REMAP primary outcome of hospital free days at 90 days after the elective surgical encounter.

8.4.2. Secondary Endpoints

All secondary endpoints as specified in the Core Protocol.

The domain-specific secondary outcome measures (occurring during the index elective surgical procedure), include:

- Hypoglycemia
- Gastrointestinal intolerance
- SAE as defined in Core Protocol
- 1 year mortality

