### 9.2. Secondary Endpoints

Secondary domain-specific outcome measures include information about EHR based alerts reported during the index elective surgical admission, perioperative outcomes, and surgical outcomes.

Specifically, they include:

- Perioperative outcomes (enrollment to postoperative 90 days)
  - Gastrointestinal intolerance (dichotomous; present/absent)
  - SAE as defined in Core Protocol (mild, moderate, severe, life threatening/disabling; adjudicated as related, possibly related, unrelated)

- Surgical outcomes
  - Index admission
    - Postoperative intensive care unit (ICU) admission (dichotomous; any admission/none)
    - ICU length of stay (LOS; continuous, days)
    - Hospital LOS (continuous, days)
    - Discharge disposition (categorical; Home, SNF/LTAC, Death/Hospice)
    - In-hospital mortality (dichotomous; yes/no)
  - 30-day outcomes
    - Organ failure free days (i.e., vasopressor exposure, hemodialysis, or mechanical ventilation; continuous, days)
    - Surgical site infection, as defined by NSQIP and the CDC (categorical)
    - Surgical site occurrence, as defined by Ventral Hernia Working Group (categorical)
  - 90-day outcomes
    - Reoperation/reintervention, both incidence and total number (dichotomous, time to event; any/none and continuous, number)
    - Readmission (dichotomous, time to event; any/none, days)
    - Venous thromboembolic events including deep vein thrombosis and pulmonary embolus after surgery (dichotomous, time to event; any/none, days)
    - Mortality (dichotomous, time to event; yes/no, days)

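### Protocol 8.4.2 confines hypoglycemia, GI intolerance and SAEs to the index procedure, against SAP 9.2, and the listed postoperative contacts do not ask about non-serious GI intolerance

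*Protocol*

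**What the plan says.** **Outcome window.** Protocol 8.4.2 introduces four items with "The domain-specific secondary outcome measures (occurring during the index elective surgical procedure), include": hypoglycemia, GI intolerance, SAEs and "1 year mortality". SAP 9.2 places GI intolerance (present or absent) and SAEs under "Perioperative outcomes (enrollment to postoperative 90 days". The Protocol's summary table has a third list: GI distress that leads to stopping the drug, lactic acidosis and hepatic dysfunction, with no index-procedure limit.

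**Dosing period.** Protocol 8.3.3 starts drug the day after the pre-operative evaluation. Under 8.3.4, short-course "subjects will receive the study drug (metformin or placebo) within 7-28 days prior to the elective surgical encounter"; intermediate-course "subjects will receive the study drug for 29-90 days prior to surgery"; the long course exceeds three months. The section adds: "All patients will receive study drug for 90 days after the surgical encounter".

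**Ascertainment.**
- Protocol 9.1.1 lists GI intolerance and SAEs among the data collected, with no timing, source or question. Hypoglycemia is not listed there or in SAP 9.2.
- Protocol 8.3.3 plans contact between the clinic visit and "surgery to evaluate study drug compliance as well as any adverse events associated with the study drug".
- Protocol 8.3.9 says "The following questionnaires should be completed during the 30-day telephone call", then names resource use, EQ-5D and return to work. The 90-day telephone list is readmission, EQ-5D, return to work, FAQ and a cognitive battery. The 90-day visit has resource use, EQ-5D, return to work, FAQ and NIH Toolbox tests.
- SAP 8 and 12 describe a compliance check at day 90, and recording of early stopping when the patient reports it.

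**The concern.** The plan gives one set of outcomes two incompatible windows. A site working from 8.4.2 would count GI intolerance only around the operation, while the analyst working from SAP 9.2 expects it from enrollment to day 90. The postoperative contacts itemised in the Protocol do not supply what the longer window needs.

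This bears on the main expected harm. Protocol 6.2.3 reports GI discomfort in 30-60% of subjects in earlier metformin studies, and SAP 4 gives poor tolerance of study drug as one reason the trial stopped. Diarrhea or loss of appetite at home is unlikely to be an SAE or to cause a readmission, so it is recorded only if someone asks or the patient volunteers it. If unasked is then read as absent, both arms look cleaner than they were and the absolute difference between them shrinks.

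**Working it through.** The plan states no figure on this point, so there is none to reproduce. The check compares the windows with the dosing period.

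**Inputs.** Postoperative dosing: 90 days (Protocol 8.3.4). Pre-operative dosing: 7-28 days (short), 29-90 (intermediate), more than 90 (long). For the long course I use 91 to 365 days, because SAP 8 admits surgery up to 365 days after randomization. Index stay: 1 to 14 days, an assumption, since the documents give none. Full courses are assumed, without suspension.

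**1. Exposure outside the 8.4.2 window.** Read generously, with the procedure taken as the whole index stay:

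share outside = (pre-operative days + 90 - stay) / (pre-operative days + 90)

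- Short: from (97 - 14)/97 = 85.6% to (118 - 1)/118 = 99.2%
- Intermediate: from (119 - 14)/119 = 88.2% to (180 - 1)/180 = 99.4%
- Long: from (181 - 14)/181 = 92.3% to (455 - 1)/455 = 99.8%

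**2. Exposure with no listed adverse-event question.** Crediting the whole pre-operative period to the 8.3.3 contact leaves at most the 90 postoperative days:

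share = 90 / (pre-operative days + 90)

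| Pre-operative days | Calculation | Postoperative share |
|---|---|---|
| 7 (short, lower) | 90/97 | 92.8% |
| 28 (short, upper) | 90/118 | 76.3% |
| 29 (intermediate, lower) | 90/119 | 75.6% |
| 90 (intermediate, upper) | 90/180 | 50.0% |
| 91 (long, lower) | 90/181 | 49.7% |
| 365 (long, SAP limit) | 90/455 | 19.8% |

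Crediting the index stay as well, by (90 - stay)/(pre-operative days + 90), gives 64-92% for the short course, 42-75% for the intermediate and 17-49% for the long.

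**3. Effect on the comparison.** If a fraction c of events is captured equally in both arms, the observed difference is c × (p1 - p0). Illustration with assumed values: true rates of 45% and 20%, c = 0.5. The observed rates are 22.5% and 10%, so the difference falls from 25 to 12.5 points. The risk ratio stays at 45/20 = 22.5/10 = 2.25. The odds ratio, the scale of the logistic model in SAP 13.2, falls from (0.45/0.55)/(0.20/0.80) = 3.27 to (0.225/0.775)/(0.10/0.90) = 2.61.

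**4. Leaving unasked as missing does not solve it.** SAP 13.5 imputes missing model data with the median within dose. For a yes/no endpoint that median is absent whenever fewer than half of those observed in the dose group report the event.

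**The case against.** The strongest reply is that an outcome window does not limit data collection. Protocol 9.1.1 collects GI intolerance and SAEs without any time limit, and SAP 9.2 analyses them to day 90. Section 8.3.9 is a questionnaire schedule introduced for cognitive and motor change, so its silence on adverse events is weak evidence that nobody asked. SAE rules are deferred to a Core Protocol that is not among the documents. The day-90 compliance check and the recording of early stopping bear on the summary table's discontinuation-based GI endpoint, and readmission and resource-use questions pick up some serious events.

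Much of this stands. A reader might infer that most of the drug exposure has no planned safety ascertainment. The documents do not support that: 9.1.1 plans collection, 8.3.3 plans a pre-surgery contact about adverse events, the SAE procedures cannot be seen, and the postoperative days are under half of long-course exposure. Days are also an imperfect proxy for events. If GI effects come early in treatment, the share of events missed is smaller than the share of days.

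What the reply leaves standing is narrower. Section 9.1.1 names a variable but no timing or question, so it neither settles the conflict between windows nor adds an item to a call. Protocol 2 keeps intervention specifics out of the Core Protocol, so a metformin-specific, non-serious symptom should be handled in this appendix. A compliance check classifies patients as continuing or not; no reason, date or symptom item is described.

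**Conclusion.** The concern holds in two parts. First, the 8.4.2 window is a wrong stated rule: it is impossible for one of its own items, contradicts SAP 9.2, and excludes roughly 86% or more of dosing days under an assumed stay of up to 14 days. Second, no listed postoperative contact systematically solicits non-serious GI intolerance, adverse events or a reason for stopping. The affected 90 days are 76-93% of short-course, 50-76% of intermediate-course and under 50% of long-course exposure.

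The likely consequence is an understated absolute GI difference. Its size is unknown: the halving shown above rests on assumed rates and on equal capture in both arms, under which the risk ratio would not change. Nothing can be concluded about SAE capture without the Core Protocol, and the definition of the primary endpoint, hospital-free days, is not touched. The matter should be corrected, but it does not undermine the main analysis.

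**What to change.** 1. In Protocol 8.4.2, replace the index-procedure window with enrollment to postoperative day 90 for GI intolerance and SAEs, and give 1-year mortality its own window.
2. Reconcile the GI definition across the Protocol summary (distress leading to discontinuation), 8.4.2 and SAP 9.2. Either add hypoglycemia to 9.1.1 and SAP 9.2, or remove it from 8.4.2.
3. Add a short fixed item set to the existing 30-day contact and to both forms of the 90-day contact: drug status, stop date and reason, GI symptoms, other adverse events.
4. For data already collected, have the SAP state how and when postoperative GI data were obtained. It should not code unasked as absent, directly or through the median imputation in SAP 13.5. Reporting the pre-surgery period, where questions were planned, separately from the postoperative period would make the difference in capture visible.

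The SAP was finalized on 06 September 2023, after the trial had been discontinued. Item 3 therefore cannot recover data for this analysis and serves only continued use of the appendix; item 4 is the part that can still change what is reported. The cost is a wording change, a few minutes per scheduled contact, and GI rates that may look less favourable.
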